3. STUDY DESIGN OVERVIEW

Sequential Allocation of Subject Numbers	
	Fluarix Tetra (N=max 1,440 (720 vaccinees \geq 3 years old, 720 vaccinees between 6-35 months old))
Vaccination (Fluarix Tetra)	Drug Use Investigation Conclusion 21 days (Day 0 to Day 20) follow-up after vaccination with Fluarix Tetra
N: Number of subjects planned to be enrolled	

Drug use investigation conclusion will depend on the 21 days contact of the subject in the drug use investigation. Definition of Conclusion of drug use investigation for a subject: A subject who is available for the concluding follow-up contact 21 days (Day 0 to Day 20) after receiving *Fluarix Tetra* is considered to have completed the drug use investigation.

- Drug use investigation design: A prospective, observational, non-comparative, multi-center study in Korea.
- Vaccination schedule: Vaccination as per locally approved PI (which is not part of the drug use investigation): to adults and previously vaccinated children aged \geq 6 months, a single 0.5 ml dose of *Fluarix Tetra* will be administered. To previously unvaccinated children aged 6 months to $<$ 9 years, two doses will be administered with a second 0.5 ml dose at least 4 weeks apart from the first one as per the local PI in Korea.

Fluarix Tetra may be administered to pregnant women/lactating women as per PI, if there is a clear need. Pregnancy outcome (whether full-term or premature, information on the status of the mother and child) in vaccinated pregnant subjects will be followed-up at 6-8 weeks after delivery, if possible.

Note:

- Vaccination with *Fluarix Tetra* is not part of the drug use investigation.
- Signature of the subject/subject's parent(s)/LAR(s) on the ICF/IAF signify enrolment of the subject into the drug use investigation. The ICF/IAF is for the collection and handling of safety information and not for the vaccination procedure.

- Administration of vaccines included in the EPI and other licensed vaccines are allowed in this drug use investigation regardless of the time of administration.
- Safety monitoring:
 - Recording of all AEs during the 21 days (Day 0 to Day 20) using diary cards after *Fluarix Tetra* is administered.
 - The participating physician will transcribe the collected information into the CRF in English.
 - ***Recording of all ADRs reported during the 21 days (Day 0 to Day 20) follow-up period after administration of Fluarix Tetra***

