 - Recording of SAEs from the date of vaccination until 21 days (Day 0 to Day 20) after *Fluarix Tetra* is administered during the subject's participation in the study.
 - All AEs , ADRs and SAEs starting immediately following administration of *Fluarix Tetra* must be recorded onto the CRF and all ADRs and SAEs must be reported using the ADR reporting form and SAE reporting form, the latter to be sent to GSK according to the required timelines, irrespective of intensity or whether or not they are considered vaccination-related.
 - Parents of children aged 6 months to <12 years wil be contacted to provide details of any AEs experienced by the children 21 days after the children receives the vaccination.
 - Subjects for whom diary card transcription into CRF will be done through phone contact are considered to have completed the drug use investigation.
- Blood Samples: No blood samples will be collected in this drug use investigation.
- All subjects who receive at least one dose of the *Fluarix Tetra* and can be evaluated for whether the subject experienced an AE will be included in the safety population. For each subject, this drug use investigation will include a single or two visits and a follow-up contact 21 days (Day 0 to Day 20) after each vaccination with *Fluarix Tetra*.
- Pregnant subjects who receive *Fluarix Tetra* or subjects who become pregnant within 21 days after vaccination with *Fluarix Tetra* will be followed to determine the outcome of the pregnancy, if possible. At the end of the pregnancy, whether that be full-term or premature, information on the status of the mother and child will be forwarded to GSK, if possible. Generally, follow-up should be no longer than 6 to 8 weeks following the EDD, if possible.
- Duration of the drug use investigation:
 - 6 years (for children 36 months and above and adults).
 - 4 years (for children from 6 to 35 months of age)
- Type of drug use investigation: Self-contained.

- Data collection: Standardised hard copy CRF (SAEs, ADRs, Pregnancy information will be collected by using the SAE, ADR, Pregnancy Reporting Form).

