4.1.1. Recruitment at study centers

- This prospective, observational drug use investigation will be conducted at multiple centers (mainly in hospitals and private clinics) in Korea.
- Study population: Subjects aged \geq 6 months who receive *Fluarix Tetra* as a part of routine practice at a private clinic or hospital. Only subjects to whom *Fluarix Tetra* is administered in routine clinical practice will be invited to participate in the drug use investigation.
- Eligible subjects will join the drug use investigation after the ICF/IAF has been signed by the subject/subject's parent(s)/LAR(s).
- The drug use investigation is required to be conducted in at least one hospital with IRB oversight in order for the drug use investigation to be conducted in private clinics with no IRB.
- The vaccine will be purchased by the subject/subject's parent(s)/LAR(s).
- The recruitment will be monitored by the study monitor.

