4.2. Inclusion criteria for enrolment

All subjects must satisfy the following criteria at drug use investigation entry:

- Male or female subjects who were vaccinated with *Fluarix Tetra* or eligible to receive *Fluarix Tetra* according to the locally approved PI.

Note: According to current approved PI, the subjects below are included.

Subjects	1 st dose	Follow-up contact after 21 days	2 nd dose	Follow-up contact after 21 days
Primed	●	●		
Unprimed ¹	●	●	●	●
Unprimed ²	●	●		
Unprimed with history of Fluarix Tetra ³			●	●

- Primed: adults and previously vaccinated children aged ≥ 6 months
- Unprimed: previously unvaccinated children aged 6 months to <9 years

¹ Unprimed children who participate in the drug use investigation following the administration of both doses of *Fluarix Tetra*

² Unprimed children who participate in the drug use investigation following the administration of the first dose of *Fluarix Tetra*

³ Unprimed children who participate in the drug use investigation following the administration of the second dose of *Fluarix Tetra*

- 2nd dose would be given at least 4 weeks after the 1st dose.
- Signed informed consent as ICF/IAF obtained from the subject/subject's parent(s)/LAR(s).

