6.5. Detailed description of study procedures

6.5.1. Procedures prior to study participation

6.5.1.1. Informed consent

The ICF/IAF for this drug use investigation is for the collection and handling of personal and safety information after vaccination with *Fluarix Tetra*. Diary cards will be used to collect safety information and for SDV. The ICF/IAF for this drug use investigation will not include consent for vaccination as vaccination is at the discretion of the subject/subject's parent(s)/LAR(s) and the physician. Informed consent may be taken after the vaccination. Parent(s)/LAR(s) who agree to have their eligible children participate in this drug use investigation will return the diary card to physician and accept a telephone interview from physicians for collection of safety information. Information collected will be treated confidentially and for the purpose of reporting SAE(s) to KIDS, and for public disclosure, if required.

Before performing any other study procedure, the signed informed consent as ICF/IAF of the subject/subject's parent(s)/LAR(s) must be obtained.

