All AEs, ADRs and SAEs starting immediately following administration of *Fluarix Tetra* must be recorded onto the CRF and all ADRs and SAEs must be reported using the ADR reporting form and SAE reporting form, the latter to be sent to GSK according to the

required timelines, irrespective of intensity or whether or not they are considered vaccination-related.

The standard time period for collecting and recording SAEs will begin at the receipt of *Fluarix Tetra* in the drug use investigation and will end 21 days following administration of *Fluarix Tetra* for each subject. See Section 7.3 for instructions on recording and reporting SAEs.

An overview of the protocol-required reporting periods for AEs, ADRs, SAEs and pregnancies is given in

Table 2.

Table 2 Reporting periods for adverse events, adverse drug reaction, serious adverse events, and pregnancies

Drug use investigation activity	Vaccination	21 days (Day 0 to Day 20) post-vaccination
Reporting of AEs (expected & unexpected)	●	●
Reporting of ADRs	●	●
Reporting of SAEs	●	●
Reporting of pregnancies *	●	●

* Subjects who are pregnant and receive *Fluarix Tetra* or subjects who become pregnant within 21 days after receiving *Fluarix Tetra* in the drug use investigation, the pregnancy outcome (whether full-term or premature, information on the status of the mother and child) of these subjects will be followed-up for 6-8 weeks after delivery, if possible.

Note: Post-vaccination AEs will be collected and reported only for *Fluarix Tetra* received under the drug use investigation procedure (after signing the ICF/IAF).

All AEs/ADRs/SAEs reported within 21 days (Day 0 to Day 20) of administration of *Fluarix Tetra* within the drug use investigation need to be recorded in the CRF. These AEs/ADRs/SAEs will be classified as expected/unexpected at the time of statistical analyses (refer to [GLOSSARY OF TERMS](#) for definitions of expected/unexpected AEs).

Note: Assessment of causality and outcome will be performed by the physician according to the following classification. Causality will be assessed as: Certain; Probable/Likely; Possible; Not-Related; Conditional/ Unclassified; Unassessable/Unclassifiable. Outcome will be assessed as recovered; not recovered; recovering; resolved with sequelae; fatal; unknown.

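### Read literally, the note under Table 2 in Protocol 7.2.1 drops adverse events after a dose given before consent, although the protocol allows consent after vaccination

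*Protocol*

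**What the plan says.** The disputed rule is the note under Table 2 in Protocol 7.2.1. It says that post-vaccination adverse events are collected and reported only for vaccine "received under the drug use investigation procedure (after signing the ICF/IAF". This is current text; the Amendment 3 change summary carries the note unchanged.

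Other current passages deal with consent, eligibility and the start of recording:

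- **Consent timing.** Protocol 6.5.1.1: "Informed consent may be taken after the vaccination". Footnote 1 to Table 1 (Section 6.4) says the same. Section 6.5.1.1 also requires signed consent before any other study procedure.
- **What consent covers.** Protocol Section 3: "The ICF/IAF is for the collection and handling of safety information and not for the vaccination procedure". The same list of notes places vaccination outside the investigation.
- **Who is eligible.** The first inclusion criterion in Section 4.2 opens with "Male or female subjects who were vaccinated with" the vaccine. Footnote 3 of that section describes "Unprimed children who participate in the drug use investigation following the administration of the second dose of" the vaccine.
- **When recording starts.** The opening of Section 7.2.1 requires "All AEs, ADRs and SAEs starting immediately following administration of" the vaccine to be entered on the CRF. Section 3 has the same requirement under safety monitoring.

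**The concern.** The bracket in the note is attached to the receipt of the vaccine, not to the act of collecting data. As written, a dose counts only if the form was signed before it was given. A subject who is vaccinated in routine practice and signs afterwards follows a path that the protocol permits. Under the note, none of that dose's events would be collected or reported.

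Safety is the only objective (Protocol Section 2), so a rule on which events count bears directly on the endpoint. Sites also have to choose which passage to follow. One site may apply the note because it carries the restrictive word *only* and sits directly beneath the reporting-period table. Another may apply the opening of the same section. They would then treat the same subject differently.

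**Working it through.** No stated figure depends on this point, so the check is a comparison of texts. It takes the possible orders of dose and signature and asks what the note requires and what the other passages require.

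| Case | Note under Table 2, read literally | Other passages | Agree? |
|---|---|---|---|
| A. Consent, then dose | Events collected | Section 3 and opening of 7.2.1: recorded from administration | Yes |
| B. Dose, then consent | No events collected for that dose | 6.5.1.1 and Table 1 footnote 1 permit this order; 4.2 makes the subject eligible; Section 3 and opening of 7.2.1: recorded from administration | **No** |
| C. First dose outside the investigation, then consent, then second dose | Second dose covered, first dose not | The 4.2 table shows follow-up after the second dose only | Yes |
| D. First dose outside the investigation, then second dose, then consent | Neither dose covered | The 4.2 table shows follow-up after the second dose; 6.5.1.1 permits late consent | **No** |

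**Cases A and C.** The note does no harm here. Case C also shows what it is probably for: keeping a dose that nobody followed out of the safety data.

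**Cases B and D.** The note sorts doses by whether the signature came first. What is needed is to sort them by whether the dose is followed in the investigation. In case D the child would lose the one dose for which follow-up is planned.

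**Strength of each conflict.**

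1. Direct: Section 6.5.1.1, Table 1 footnote 1 and the inclusion criterion in Section 4.2. Each allows a sequence that the note excludes.
2. Poor fit: Section 3, which puts vaccination outside the investigation, so it is unclear how a dose can be received under an investigation procedure. The same holds for Section 4.1.1, where only subjects to whom the vaccine "is administered in routine clinical practice will be invited to participate in the drug use investigation". The requirement in Section 3 and the opening of 7.2.1 to record from administration also fits poorly.
3. Not contradictions: Section 6.5.3.9, Table 2 itself and SAP 5.1 only set the Day 0 to Day 20 window. The SAE sentence in 7.2.1 and the sentence following the note each carry their own limit to vaccine given in or within the investigation.

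**Does the SAP settle it?** SAP 3.1 lists the exclusions from the safety set. Items (1) and (2) turn on the contract date. Item (3) removes subjects who did not receive the vaccine within the study, a term that it does not define. No item removes a subject for being vaccinated before consent, and the asterisked text keeps children under 9 who enter with a second dose. The SAP neither adopts the literal note nor rules it out.

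**The case against.** The best defence is that the note can be read in harmony with the rest. Signature marks enrolment (Section 3), and no study procedure may precede it (6.5.1.1). The bracket could therefore mean only that data are gathered once consent is signed, and only for the dose that the subject enrolled for. That reading respects late consent and still leaves out an off-study first dose. It is probably what was intended, but the sentence does not say it: the bracket qualifies receipt of the vaccine.

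Other passages also limit the practical effect. Section 7.2.2.1 tells physicians to collect any adverse event and to ask about changes since the vaccine was received. Table 1 puts consent, vaccination details and diary cards in one enrolment contact, which suggests that late consent often falls at the vaccination visit. Section 4.2 still allows later entry. These points stand, and they are why the effect may be small.

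Three stronger inferences are tempting, and the documents do not support them:

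- **That the SAP removes these subjects.** It has no such exclusion. Loss through SAP 3.1(4), the item on unknown adverse event status, would require a site to enrol a subject and then record no status.
- **That the adverse event proportion would be understated by a known amount.** Late-consent subjects would have to stay in the denominator as having no event when nothing was collected, whereas SAP 3.1(4) excludes unknown or missing status. Any figure would rest on an assumed late-consent share, an assumed event rate and an assumed complete loss of events.
- **That a group would fall below 600.** The margin is 720 − 600 = 120 per group, or 120/720 = 16.7%. That measures the recruitment plan, not this note. The plan's own 20% dropout already gives 720 × 0.80 = 576.

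**Conclusion.** The point holds as a conflict of wording in current text. Read literally, the note excludes adverse events after a followed dose given before signature, while Sections 4.2, 6.4 (Table 1 footnote 1) and 6.5.1.1 make that sequence permissible. It arises only for subjects who consent after vaccination; where consent comes first, the passages agree.

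Its size is unknown. The documents give no share of subjects consenting after vaccination and do not show how sites apply the note, so no loss of subjects and no bias in the reported proportions can be claimed. The case for correcting it is that a stated collection rule conflicts with the study's sole objective, that sites could apply it differently, and that the repair is very cheap.

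**What to change.** Replace the note under Table 2 in Protocol 7.2.1 with wording such as:

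> Once the ICF/IAF is signed, AEs/ADRs/SAEs are recorded for each Fluarix Tetra dose followed in the investigation, covering Day 0 (administration) to Day 20, including events that began between that dose and signature when consent was taken after vaccination. Doses not followed in the investigation are not covered.

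This keeps the rule in 6.5.1.1 that signed consent precedes any other study procedure, because recording starts only after signature even though the period covered starts at the dose. It also keeps the note's likely purpose, since an earlier dose outside the investigation stays excluded.

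In SAP 3.1(3), state that receipt of the vaccine within the study includes a followed dose given before signature.

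The cost is a wording change to one protocol note and one SAP item, with no new data collection and no extra analysis.

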7.2.2. Evaluation of adverse events, adverse drug reactions and serious adverse events

7.2.2.1. Active questioning to detect adverse events, adverse drug reactions and serious adverse events

The physician needs to collect information on any AE in the subject. At the time of analysis, an assessment on whether the AE is expected (contained in the local PI) or unexpected (not contained in the local PI) will be done by GSK.

As a consistent method of collecting safety information, the subject/subject's parent(s)/LAR(s) should be asked a non-leading question such as:

'Have you acted differently or felt different/has your child acted differently or felt different in any way since receiving the vaccine or since the last visit?'

When an AE/SAE occurs, it is the responsibility of the physician to review all documentation (e.g. hospital progress notes, laboratory, and diagnostics reports) relative to the event. The physician will then record all relevant information regarding an AE/**ADR**/SAE on the CRF, ADR Report Form or SAE Report Form as applicable. It is not acceptable for the physician to send photocopies of the subject's medical records to GSK Vaccines instead of the appropriate completed AE/SAE pages on the CRF. However, there may be instances when copies of medical records for certain cases are requested by GSK Vaccines. In this instance, all subject identifiers will be blinded on the copies of the medical records prior to submission to GSK Vaccines.

The physician will attempt to establish a diagnosis pertaining to the event based on signs, symptoms, and/or other clinical information. In such cases, the diagnosis should be documented as the AE/**ADR**/SAE and not the individual signs/symptoms.

[figure not shown]
7.2.2.2. Assessment of intensity

Intensity of the following AEs will be assessed as described:

The physician will assess the maximum intensity that occurred over the duration of the event for all other AEs, including **ADR and SAEs** reported during the drug use investigation. The assessment will be based on the physician's clinical judgement.

The intensity of each AE, **ADR** and SAE recorded in the CRF, **ADR Report form** or SAE Report Form, as applicable, should be assigned to one of the following categories:

CCI - This section contained Clinical Outcome Assessment data collection questionnaires or indices, which are protected by third party copyright laws and therefore have been excluded.

An AE that is assessed as Grade 3 (CCI) should not be confused with a SAE. Grade 3 is a category utilised for rating the intensity of an event; and both AEs and SAEs can be assessed as Grade 3. An event is defined as 'serious' when it meets one of the pre-defined outcomes as described in Section 7.1.3.

7.2.2.3. Assessment of causality

The physician is obligated to assess the relationship between *Fluatrix Tetra* and the occurrence of each AE/SAE. The physician will use clinical judgement to determine the relationship. Alternative plausible causes, based on natural history of the underlying diseases, concomitant therapy, other risk factors, and the temporal relationship of the event to *Fluarix Tetra* will be considered and investigated. The physician will also consult the local PI for marketed products in the determination of his/her assessment of AEs.

There may be situations when a SAE has occurred and the physician has minimal information to include in the initial report to GSK Vaccines. However, it is very important that the physician always makes an assessment of causality for every event prior to submission of the SAE to GSK Vaccines. The physician may change his/her opinion of causality in light of follow-up information, amending the SAE information accordingly. The causality assessment is one of the criteria used when determining regulatory reporting requirements.

In case of concomitant administration of multiple vaccines, it may not be possible to determine the causal relationship of general AEs to the individual vaccines administered. The physician should, therefore, assess whether the AE could be causally related to vaccination rather than to the individual vaccines.

Causality of AEs should be assessed by the physician using the following question:

Is there a reasonable possibility that the AE may have been caused by *Fluarix Tetra*?

Non-serious and serious AEs will be evaluated as two distinct events. If an event meets criteria to be determined ‘serious’ (see Section 7.1.3), additional examinations/tests will be performed by the physician in order to determine ALL possible contributing factors applicable to each SAE.

Possible contributing factors include:

- Medical history
- Other medication
- Protocol required procedure
- Other procedure not required by the protocol
- Lack of efficacy of the vaccine(s), if applicable
- Erroneous administration
- Other cause (specify)

NOTE: The use of the term “drug” here refers to *Fluarix Tetra*.

The relationship of the drug to an AE will be determined by the physician based on the following definitions:

1. Certain:
 - The relationship of the administration and use of the drug is reasonable and it is not able to be explained by other medication, chemical substances or concomitant disease, it shows clinically reasonable response on withdrawal of the drug, the decisive case in the pharmacological or phenomenological aspect on re-challenge of the drugs if needed.
2. Probable/Likely:
 - The temporal sequence of the administration and use of the drug is appropriate and it does not seem that it is accompanied by other medications, chemical substances or concomitant disease, in the case that shows clinically appropriate response on withdrawal of the drug (no information for re-challenge).
3. Possible:
 - The temporal sequence of the administration and use of the drug is appropriate but it is also able to be explained by other medications, chemical substances or concomitant disease, and information related to withdrawal of the drug is insufficient or vague.
4. Not-Related:

- The AE is not related to the drug if there is evidence that clearly indicates an alternative explanation. If the subject has not received the drug, the timing of the exposure to the drug and the onset of the AE are not reasonably related in time, or other facts, evidence or arguments exist that reasonably suggest an alternative explanation, then the AE is not related.

5. Conditional/Unclassified:

- In the case that more information is needed for a proper evaluation or additional information is under review.

6. Unassessable/Unclassifiable:

- In the case that could not be judged due to insufficient or conflicting information and no way to complement or validate.

